8.2 Control Group: Conventional Lung-Protective Ventilation (LPV)

Patients randomized to the control group will be treated with the same explicit standard ventilation protocol that we used to good effect in several recent multi-centre trials in ARDS. The overall goals for this strategy are to minimize volutrauma and atelectrauma to the extent possible with standard of care ventilation.

Volume Assist Control will be the default mode and will be set to achieve lower tidal volumes (6ml/kg PBW) and plateau pressures ($P_{PLAT} \leq 30$ cm H₂O). Other modes may also be used at the discretion of the attending physician. The same limits to P_{PLAT} and V_T apply regardless of ventilator mode. Only when the patient is being ventilated with Pressure Support of 10 cm H₂O support or less and with PEEP ≤ 8 cm H₂O and FiO₂ ≤ 0.4 will these thresholds (P_{PLAT} and V_T) no longer apply. We recommend that PEEP and FiO₂ be adjusted according to oxygenation targets using the higher PEEP-FiO₂ table, allowing for use of lower PEEP if clinically indicated. If the plateau pressure target is exceeded, V_T will be reduced as needed to a minimum of 4 ml/kg PBW, and/or PEEP reduced and FiO₂ increased as necessary to achieve $P_{PLAT} \leq 30$ cm H₂O while providing adequate oxygenation.

If a patient's state worsens and meets entry criteria from the EOLIA trial (persistence of either $\text{PaO}_2/\text{FiO}_2 < 80$ or $\text{pH} < 7.15$ and $\text{PaCO}_2 > 60$) they can receive VV-ECMO (a secondary outcome) at the discretion of the attending physician.

8.3 Procedures Common to Both Groups – Experimental & Control

For patients in both groups, we will protocolize:

1. Weaning from mechanical ventilation;
2. Prone positioning: a procedure that places the patient face-down for 16-20 hours per day, will be applied daily to patients whose $\text{PaO}_2/\text{FiO}_2$ remains < 150 during the first week as dictated by evidence-based practice for the management of hypoxemia and clinician discretion; and
3. Intravenous fluid therapy for patients not in shock. For these patients, a conservative fluid approach will be applied, since this strategy has been shown to reduce the duration of mechanical ventilation for patients with ARDS.

To ensure timely discontinuation of mechanical ventilatory support, all patients in either group not receiving ECMO at that time will be assessed daily for standard “readiness to wean” criteria. In patients who meet these criteria, an SBT will be performed with no or minimal mechanical ventilation support and those that pass will be promptly extubated (Manual of Procedures).

8.4 Crossovers

We will sub-classify crossovers as consistent with, or in deviation of, the study protocol and will collect detailed reasons for crossovers classified as protocol deviations. Crossovers that are consistent with the protocol include control group patients who receive the ECMO intervention (experimental group) once they meet the ECMO criteria of hypoxemia (section 7.2) and as part of rescue therapy, or when ECMO is discontinued before day 7 in the experimental group after passing a sweep gas off trial (section 7.1.2). Crossovers that are in deviation of the protocol will include Conventional Lung-Protective Ventilation (control group) patients being treated with ECMO when not allowed by protocol (do not meet the criteria defined in sections 7.2/3.2/3.3) and ultra-protective ventilation (experimental group) patients who stop the ECMO intervention prematurely.

8.5 ECMO Study Device Supply

Supply of the device will be outlined in the site agreement.

9 SAFETY AND REPORTING REQUIREMENTS

The critically ill patient population are admitted to the ICU for life-sustaining therapies (e.g. mechanical ventilation, vasopressors, renal replacement therapy). Many of the potential subjects will be admitted with the expectation of receiving end-of-life care and possibly dying in the ICU. Furthermore, medical complications are likely to occur in this population, consistent with the nature of their progressive illness (e.g. nosocomial infections; septic shock; multi-organ failure; need for vasopressors; acute renal failure and the need for renal replacement therapy; arrhythmias; cardiac arrest; coma; aspiration; venous thromboembolism). Due to these relatively unique morbidity and mortality expectations in the critically ill patient population and the intervention's safety profile, generic adverse events will not be collected for this study and only study-procedure related SAEs will be collected and reported (see section below). Expected events occurring in the course of life-support patient, and not related to study procedure, will not be reported as SAEs in the ULTIMATE trial.

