9.1 Serious Adverse Event

A serious adverse event (SAE) in the ULTIMATE trial is defined as:

- a) any event that is fatal or immediately life threatening, permanently disabling, severely incapacitating, or requires prolonged inpatient hospitalization,
OR...
- b) any event that may jeopardize the patient and requires medical or surgical intervention to prevent one of the outcomes listed above,
AND...
- c) which the attending physician believes to be **related*** to a study procedure

**A related event is an event in which there is a reasonable possibility that the study procedure caused or contributed (definitely, probably, or possibly) to the SAE; this conclusion may be supported by the following observations, though these are not required for the determination of relatedness:*

- *There is a plausible time sequence between onset of the SAE and study procedure;*
- *There is a plausible biological mechanism through which study procedure may have caused or contributed to the SAE;*

The SAEs dictated below are of *particular interest*; however, they are not an exhaustive list of all SAEs that might be identified and reported on the trial (please refer to section 8.2- evaluation of safety for further details):

- death due to the ECMO device (failure, accident, septic shock due to infection at the cannulation site, hemorrhagic shock due to bleeding at the cannulation site, intracranial hemorrhage, massive circuit clotting)
- cardiac arrest due to massive circuit clotting, pneumothorax during cannula insertion, or ECMO device failure/accident
- massive hemorrhage requiring transfusion of ≥ 10 packed red blood cells
- massive gaseous (air) emboli

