10.2 Evaluation of Safety

The safety and tolerability of VV-ECMO will be evaluated by means of recording SAEs in both groups and monitoring the predicted physiological response (reduced driving pressure ΔP) to CO₂ removal by VV-ECMO.

The following safety outcomes will be evaluated:

- Mechanical complications
- Hemorrhagic complications
- Renal complications
- Cardiovascular complications
- Pulmonary complications
- Metabolic complications
- Neurological complications
- Infections
- Death
- Clinical endpoints as defined in section 9.10.

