10.12 Proposed Frequency of Analyses

Due to the small size and short duration of this pilot RCT, we have not planned for any domain-specific interim analyses. We have planned, however, to provide the Data Safety and Monitoring Board (DSMB) with analyses by group at the completion of this pilot RCT. Further details regarding DSMB commitment will be detailed in the DSMB charter. These analyses will include relative use of neuromuscular blockade, sedative infusions, and vasopressor infusions; and relative rates of prone positioning, ECMO, and mortality. In this pilot RCT, we will not undertake any formal statistical inference or testing and will report descriptive statistics as required. We

will also consider controlling for centre and providing both unadjusted analyses and analyses adjusted for age and baseline oxygenation, and duration of ventilation prior to enrolment using Bayesian (generalized) linear models. The results from these models will be summarised using the posterior mean and 95% credible intervals. All these analyses will include all randomised patients adhering to the intention to treat principle. We will use complete case analyses, with the level of missingness reported for each outcome. Investigators will remain blinded to these clinical results, while the full ULTIMATE trial moves forward. Due to the pilot study design of the trial and its short duration, no subgroup analyses are planned.

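### Complications are recorded only if an unblinded physician judges them related to a study procedure, so the planned SAE comparison of the two groups rests on unequal ascertainment

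*Protocol*

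**What the plan says.** Section 9 limits collection, not just expedited reporting. Generic adverse events are not collected and "only study-procedure related SAEs will be collected and reported". It adds: "Expected events occurring in the course of life-support patient, and not related to study procedure, will not be reported as SAEs in the ULTIMATE trial". Its examples of such expected complications include hospital-acquired infection, acute renal failure, arrhythmia, cardiac arrest, coma and venous thromboembolism.

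Section 9.1 makes relatedness part of the SAE definition. An event qualifies only if it is one "which the attending physician believes to be" related to a study procedure. The threshold is low: it is enough that "there is a reasonable possibility that the study procedure caused or contributed (definitely, probably, or possibly) to the SAE". The term study procedure is not defined.

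Section 10.2 says that the safety of VV-ECMO will be "evaluated by means of recording SAEs in both groups", together with the driving-pressure response. It then lists ten outcomes: mechanical, hemorrhagic, renal, cardiovascular, pulmonary, metabolic and neurological complications, infections, death, and the clinical endpoints. Section 10.9 makes SAE frequency and type an exploratory endpoint.

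Section 5 describes the trial as open-label. Section 10.12 provides the DSMB "with analyses by group at the completion of this pilot RCT". The contents it lists are drug use, proning, ECMO and mortality, and no complication counts.

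**The concern.** Whether an event enters the database depends on a judgement that is likely to differ by arm. A serious bleed or infection in a cannulated, heparinized patient is easily called possibly related to ECMO. The same event in a patient on standard ventilation is easily put down to the illness and, under section 9, is then not recorded. A by-arm SAE table built this way mixes true risk with the probability of attribution.

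Sections 9 and 9.1 also conflict with section 10.2. One part leaves unrelated complications uncollected; the other promises to evaluate those same classes in both groups. No analysis plan can repair this later, because the events will not be in the data.

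What is at stake is the harm information from the pilot. Bleeding is a harm that the protocol itself emphasizes: section 3.2 uses hemolysis or bleeding rates to justify the type of device, and section 8.1.2 recommends heparin. Barotrauma is a secondary question of the definitive trial (section 4.1), into which these patients roll over if feasibility is shown and no major change is needed (section 4.2).

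**Working it through.** The protocol states no SAE rate, so there is no figure to reproduce. The check has two parts.

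**1. What is recorded without a relatedness judgement.** Each outcome in section 10.2 is set against sections 6.1, 6.2, 7 and 10.10. Many of the daily laboratory values are reported only if done clinically.

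| Outcome in 10.2 | Recorded in both arms regardless of attribution | Recorded only as a related SAE |
|---|---|---|
| Death | ICU, hospital and 6-month status | – |
| Clinical endpoints | ICU stay, ventilation duration, ventilator-free days | – |
| Renal | Renal replacement therapy, creatinine, SOFA | Other renal events |
| Cardiovascular | Hemodynamics, vasopressors, inotropes, SOFA | Arrhythmia, arrest, thromboembolism |
| Pulmonary | Daily respiratory data, blood gases | Barotrauma |
| Metabolic | Chemistry, blood gases | Other metabolic events |
| Neurological | Daily GCS, 6-month Rankin scale | Stroke, intracranial hemorrhage |
| Hemorrhagic | Hemoglobin, platelets | Bleeding events |
| Infections | Temperature, white cell count | All infection events |
| Mechanical | None | All; if device-related, mainly with ECMO |

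Two of the ten outcomes are fully covered. Five have partial proxies. Bleeding and infection have only laboratory values or vital signs, and no event record. Transfusion does not appear in the schedule.

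The layout of section 9.1 (a or b, and c) could be read as applying relatedness to b alone. Section 9 settles that it applies to every SAE.

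**2. How large the distortion could be.** Inputs: n = 72/2 = 36 per arm (sections 10.1 and 10.15). Assumed, because the protocol gives no values: the same true risk r of a serious complication in both arms, 20–50%; attribution a of 0–10% in control and 50–80% in the ECMO arm; at most one event per patient.

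Expected reports per arm = 36 × r × a. Spurious risk difference = r × (a_ECMO − a_control). Chance of no control report = (1 − r × a_control)^36.

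- r = 30%, a_control = 5%: control 36 × 0.30 × 0.05 = 0.54. ECMO 36 × 0.30 × 0.50 = 5.4, up to 36 × 0.30 × 0.80 = 8.64. Difference 0.30 × 0.45 = 13.5 points, up to 0.30 × 0.75 = 22.5 points. Chance of no control report: (1 − 0.015)^36 = 58%.
- Smallest difference in the range: 0.20 × (0.50 − 0.10) = 8 points.
- Largest: 0.50 × (0.80 − 0) = 40 points.
- Over the range, control expects 0 to 36 × 0.50 × 0.10 = 1.8 reports, and ECMO 36 × 0.20 × 0.50 = 3.6 to 36 × 0.50 × 0.80 = 14.4.
- Equal attribution, for example 50% in both arms: difference 0.
- Collection regardless of attribution, at r = 30%: 36 × 0.30 = 10.8 expected in each arm, difference 0.

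**The case against.** The strongest defense is that the filter is reasoned. Section 9 explains that critically ill patients have many serious events from their illness. SAEs are exploratory here, no formal inference is planned (sections 10.1 and 10.12), and none of the three criteria in section 10.13 uses them. All of this is true, and it lowers the severity. It justifies limiting expedited reports. It does not justify leaving a short list of serious complications unrecorded in 72 patients whose data are already collected daily, and a descriptive table with unequal ascertainment still misleads.

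Four stronger readings are tempting, and the documents do not support them.

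- *The control arm reports almost no SAEs by construction.* Control ventilation follows an explicit protocol (section 8.2). Weaning, proning and fluids are protocolized in both arms (section 8.3). Rescue ECMO is allowed, and possible relatedness suffices. Two of the four SAEs of particular interest, massive hemorrhage and massive air emboli, are not worded around ECMO. Control SAEs can therefore occur; low counts are a likely result of attribution, not a rule.
- *Most safety outcomes are uncollected.* The table above shows otherwise. The gap is in complication events.
- *A modest true excess would appear as a twelvefold one.* With true risks of 20% and 15% and attribution of 90% and 10%, the apparent ratio is (0.20/0.15) × (0.90/0.10) = 12. Of this, the factor 9 is simply the assumed attribution ratio.
- *The DSMB has no comparison by arm during enrolment.* Section 10.12 rules out only domain-specific interim analyses and defers details to a charter that is not shown. Section 9.3 sends each initial SAE report to the DSMB chair within one business day of receipt.

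**Conclusion.** The point holds in a limited form. Sections 9 and 9.1 make an unblinded relatedness judgement the condition for recording a complication, while section 10.2 plans to evaluate those complications in both groups. These sections must be reconciled. As written, SAE frequencies for bleeding, infection, thromboembolism and barotrauma are not comparable between arms, and the control count is likely to be the lower one.

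The direction rests on attribution being more frequent in the ECMO arm, which the text invites but does not fix. The size cannot be taken from the protocol: 8 to 40 points under the stated assumptions, and zero under equal attribution. The Manual of Procedures and the case report forms are not at hand. If they already record these events in both arms, the data gap closes, but the text of section 9 would still contradict them. Severity: should-fix.

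**What to change.** Amend sections 9, 9.1 and 10.2 so that they agree:

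1. Record a prespecified list of serious complications, namely the classes in section 10.2 plus barotrauma and transfusion, in both arms regardless of attribution, to ICU discharge or day 30 as in section 9.4. Use definitions that do not refer to ECMO.
2. Base the by-arm description of safety on these events.
3. Keep relatedness as a separate field and as the trigger for 24-hour reporting.
4. Define study procedure for each arm.
5. Add these counts to the by-group DSMB analyses already planned in section 10.12. No extra interim look is needed for this point.

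The cost is about one CRF page on top of existing daily collection, short edits to the text, and some extra data entry at sites.

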9.1 Serious Adverse Event

A serious adverse event (SAE) in the ULTIMATE trial is defined as:

- a) any event that is fatal or immediately life threatening, permanently disabling, severely incapacitating, or requires prolonged inpatient hospitalization,
OR...
- b) any event that may jeopardize the patient and requires medical or surgical intervention to prevent one of the outcomes listed above,
AND...
- c) which the attending physician believes to be **related*** to a study procedure

**A related event is an event in which there is a reasonable possibility that the study procedure caused or contributed (definitely, probably, or possibly) to the SAE; this conclusion may be supported by the following observations, though these are not required for the determination of relatedness:*

- *There is a plausible time sequence between onset of the SAE and study procedure;*
- *There is a plausible biological mechanism through which study procedure may have caused or contributed to the SAE;*

The SAEs dictated below are of *particular interest*; however, they are not an exhaustive list of all SAEs that might be identified and reported on the trial (please refer to section 8.2- evaluation of safety for further details):

- death due to the ECMO device (failure, accident, septic shock due to infection at the cannulation site, hemorrhagic shock due to bleeding at the cannulation site, intracranial hemorrhage, massive circuit clotting)
- cardiac arrest due to massive circuit clotting, pneumothorax during cannula insertion, or ECMO device failure/accident
- massive hemorrhage requiring transfusion of ≥ 10 packed red blood cells
- massive gaseous (air) emboli

9.2 Reporting Serious Adverse Events

All serious adverse events (SAEs) as defined in section 8.1 must be recorded on case report forms. In addition, they must be reported using the SAE form and submitted to Ozmosis within 24 hours of becoming aware of the event.

All SAEs must be reported as follows:

Within 24 hours: Report initial information (on trial specific SAE report form) by e-mail to:

Ozmosis Research Inc.
[contact]
E-mail: [contact]

The initial information should always contain:

- Name of Reporter/Investigator,
- Subject Identification,
- Adverse Event Term,
- Mechanical Ventilation Type and Start/Stop Dates

Within 3 calendar days: E-mail completed trial-specific Serious Adverse Event form including;

- Any information required per the SAE report form that was not included in the initial report

- Any additional, relevant and **de-identified** clinical notes, diagnostic test results and medical interventions
- Ensure that the patient eCRF pages are complete

9.3 Procedures for Expedited Reporting

Responsibility for Reporting Serious Adverse Events to Sponsor

Ozmosis will be responsible for submitting SAE reports (Initial and/or Follow-up reports) received from the sites, to the Sponsor and the domain Principal Investigators within 1 business day after receipt of the SAE form at Ozmosis.

Reporting Serious Adverse Events to Data Safety Monitoring Board (DSMB)

Ozmosis will be responsible for submitting SAE reports received from the sites to the DSMB chair. The initial SAE report will be sent within 1 business day of receipt of the SAE form at Ozmosis, with follow-up reports and synthesis from Sponsor and Domain Principal Investigators being sent when available.

Reporting Serious Adverse Events to Local Research Ethics Boards

Investigators must follow their local Research Ethics Boards (REBs)/Institutional Review Boards (IRBs) guidelines for SAE reporting. Documentation of correspondence with REBs/IRBs should be forwarded to Ozmosis.

Documentation can be any of the following:

- letter from the REB/IRB acknowledging receipt
- stamp from the REB/IRB, signed and dated by REB/IRB chair, acknowledging receipt
- letter demonstrating the SAE was sent to the board

9.4 Reporting & Follow up of Serious Adverse Events

SAEs (as defined in section 8.1) must be reported from start of randomization to time of ICU discharge or 30 days, whichever is shorter.

The investigator shall provide follow-up information as and when available in a new follow-up SAE form. All SAEs must be followed until resolved, become chronic, or stable unless the subject is lost to follow up. Resolution status of such an event should be documented in the eCRF.

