6 STUDY PLAN

6.1 Study Schedule

Consenting eligible patients will be randomized to either the experimental group or the control group. Patients randomized to the experimental group will receive ultra-protective ventilation using ECMO. Patients requiring ventilation for longer periods may continue ventilation via ECMO or receive Conventional Lung-Protective Ventilation (LPV), as deemed necessary by the treating physician. Patients randomized to the control group will receive LPV. If the patient’s clinical status declines and meets the ECMO criteria for ventilation (as established by prior randomized clinical trials), they would be eligible to receive ECMO if their treating physician deems that appropriate. Please see sections 7.2 and 7.4 below.

Study procedures common to both groups will continue for the duration of the ICU stay up to day 30. We will collect daily data during mechanical ventilation until day 30. Thereafter, we will follow patients to the time of hospital discharge and record ICU/hospital survival. We will also assess health-related quality of life by telephone interview or via email 6 months after randomization.

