troponin, phosphate, total calcium. If not done daily per clinical standard-of-care procedures, sites are not required to have these tests done exclusively for research purposes, and this will not be considered a protocol deviation.

⁹ ABG testing will include the following parameters: pH, PaCO₂, HCO₃, base excess, SaO₂, lactate, hemoglobin.

¹⁰ Blood sample collection is optional and will proceed only if patient or their SDM signs the optional consent form.

¹¹ Patient will be on mechanical ventilation, regardless of randomization, and will be assessed daily for readiness to wean.

¹² ECMO will be administered once patient has stabilized on initial MV settings and will be maintained for at least 48 hours. If patient is unsuccessful on Sweep Gas Off Trials (SGOTs) post 48 hours, then ECMO will continue until no longer needed and per the discretion of the treating physician.

¹³ Spontaneous breathing trials (SBTs) will be conducted only when patient is deemed ready for weaning from MV and per standard of care and/or institutional guidelines.

¹⁴ Patients who have received ≥ 48 hours of ECMO therapy will be assessed daily for ECMO discontinuation with SGOTs. This assessment will be considered successful if patients tolerate SGOTs for ≥ 12 hrs with no significant hypoxemia, respiratory acidosis, or work of breathing.

¹⁵ HrQOL questionnaires (ADL and EQ-5D-5L) as well as the Modified Rankin Scale (MRS) will be administered via phone or e-mail at 6 months. Vital status (patient dead or alive) will also be reported at this timepoint.

¹⁶ SAEs will be reported at the start of randomization and for a period of up to 30 days, or while in ICU, whichever is shorter.

¹⁷ Concomitant medications listed in section 6 will only be captured, if taken.

*Daily data common to both groups will be collected for the duration of intervention administration and ICU stay and up to day 30.

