8.1.2 Maintenance and Weaning of Ultra-Protective Ventilation

Deep sedation, paralysis, and these low-intensity mechanical ventilation settings will be maintained for at least 48 hours after ECMO initiation. The clinical team will make adjustments to the VV-ECMO settings to maintain the same PaCO₂, pH and PaO₂ and SpO₂ targets as above. These adjustments to VV-ECMO sweep gas or blood flow will be dictated by ABG results drawn as clinically indicated.

On study day 3, patients will then enter the maintenance and weaning phase – neuromuscular blockade will be discontinued, and lighter sedation levels (SAS 2-3) will be targeted unless otherwise decided by the attending physician.

During the first 7 days after randomization and once neuromuscular blockade is stopped and patients are making spontaneous breathing efforts, we will use sweep gas flow (primary) and sedation (secondary) to modulate spontaneous efforts to maintain low intensity ventilation, targeting the estimated dynamic trans-pulmonary driving pressure (ΔP_{L-dyn}) and tidal volume.

Clinicians will measure patient respiratory effort by calculating ΔP_{occ} (which is always zero or negative):[26]

- Perform expiratory hold and record trough pressure with next effort (record as = PEEP if no efforts made)
- Calculate $\Delta P_{occ} = \text{trough pressure} - \text{PEEP}$
- Calculate $\Delta P_{L-dyn} = (\text{Peak airway pressure} - \text{PEEP}) - 0.67 \times \Delta P_{occ}$

To maintain $\Delta P_{L-dyn} \leq 23$ cm H₂O while maintaining a V_T of 8 ml/kg PBW or lower, the treating team will adjust in the following order: a) the mechanical ventilator, b) the sweep gas flow, and c) sedation levels. After day 7 driving pressure and V_T targets, as well as sweep gas settings will be determined by the attending physician.

We will wean ECMO prior to liberating from mechanical ventilation and provide explicit protocols for weaning ECMO (See Manual of Procedures). Briefly, patients will be assessed daily for ability to discontinue ECMO – all patients who are not paralyzed and are breathing spontaneously on sweep gas flow of 4 L/min or less, and who are receiving an FiO₂ of ≤ 0.6 on the mechanical ventilator with a PaO₂/FiO₂ > 150 will undergo a trial of sweep gas off on ECMO. ECMO will be discontinued if patients tolerate sweep gas off for at least 12 hours (i.e., no significant hypoxemia, respiratory acidosis, or work of breathing).

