Anticoagulation with intravenous heparin infusion during VV-ECMO will be recommended at a level to target aPTT 1.5-2 times normal but will be ultimately managed at the discretion of the attending physician. After 14 days, all study-mandated procedures related to ECMO will cease and ongoing management will be determined by the attending physician.

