10.14 Sites

Multiple centres will participate in the ULTIMATE pilot study. All of these centres have experience in ventilation RCTs, and most have worked closely with us in the LOVS and OSCILLATE Trials. By design, we have included a mix of high-volume ECMO centres; centres doing some ECMO; and centres that do not perform ECMO but have access to an ECMO centre for backup. This is to ensure that feasibility is generalizable and to pre-emptively identify potential roadblocks to the full trial.

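### SAE reporting closes at ICU discharge or day 30, whichever comes first, while ECMO has no stated maximum duration, so late-onset related SAEs are not collected

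*Protocol*

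**What the plan says.** **Reporting window.** Protocol 9.4 states that SAEs "must be reported from start of randomization to time of ICU discharge or 30 days, whichever is shorter". Footnote 16 of the schema in 6.2 agrees: "for a period of up to 30 days, or while in ICU, whichever is shorter".

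**ECMO exposure.** Footnote 12 of the schema sets a minimum of 48 hours. For a patient who does not pass the sweep-gas-off trials after that, "then ECMO will continue until no longer needed and per the discretion of the treating physician". Section 8.1.2 adds: "After 14 days, all study-mandated procedures related to ECMO will cease and ongoing management will be determined by the attending physician". No section states a longest run. Under 8.2, control patients who deteriorate to the stated criteria may also be cannulated: "they can receive VV-ECMO (a secondary outcome) at the discretion of the attending physician". No latest start day is given.

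**Order of weaning.** Section 8.1.2: "We will wean ECMO prior to liberating from mechanical ventilation".

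**What else is collected.** Section 9 says that generic adverse events are not collected and that only SAEs related to a study procedure are. Section 9.4 requires a reported SAE to be followed until it settles. Daily data stop by day 30. After that, 6.1 says: "Thereafter, we will follow patients to the time of hospital discharge and record ICU/hospital survival". Vital status is recorded at 6 months.

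**Use of the data.** SAE frequency and type is an exploratory endpoint (10.9). Section 10.2 makes SAE recording in both groups part of the safety evaluation. Section 10.12 rules out formal inference.

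**The concern.** The window is tied to ICU stay and a calendar cap, not to time on the device or to the period in which its complications can appear. Section 9.1 singles out device failure, fatal cannulation-site infection or bleeding, intracranial hemorrhage, massive circuit clotting, massive hemorrhage and air embolism. Several of these remain possible for as long as a patient is on circuit. An infection at a former cannulation site can declare itself on the ward.

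Two things are at stake. First, the longest ECMO runs lose SAE capture from day 30, and early ICU leavers lose it from the day they leave. An analysis plan could adjust for time at risk, but it could not recover events that were never recorded. Second, ICU length of stay is itself a listed outcome (10.10), so the length of the SAE window is a post-randomization variable. Crude counts by arm can then reflect time observed as well as event rate.

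Section 4.2 allows pilot patients to become the vanguard of the definitive trial, so the gap could carry forward.

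**Working it through.** The plan gives no figure on this point to reproduce. The main check is a comparison of the text; the arithmetic only shows a plausible scale.

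**1. Can a patient be on ECMO after the window closes?**
- Day-30 limit: yes. Study-mandated ECMO procedures end at day 14, so the cap leaves 30 − 14 = 16 further days. ECMO itself may continue at the physician's discretion with no limit, and rescue ECMO in the control arm may start late.
- ICU-discharge limit: not on the text. ECMO comes off before the ventilator, so the gap after ICU discharge concerns events that first appear after decannulation.

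**2. Is there another route by which such an event is recorded?**
- Generic adverse events: not collected (9).
- Follow-up until the event settles (9.4): applies only to SAEs already reported, not to new ones.
- Daily data: stop by day 30 (6.1, 6.2).
- Safety categories in 10.2: listed without a collection window of their own.
- Hospital survival and 6-month vital status: record that a late death occurred, but not whether the device caused it. Non-fatal late events have no route.

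**3. How many patients might still be on ECMO at day 30?** The protocol gives no run length, so the medians m below are assumptions. With 72 patients randomized 1:1, expect 72/2 = 36 in the experimental arm. Runs are counted from randomization and death is ignored.
- Exponential runs: P(T > 30) = 0.5^(30/m).
- Lognormal runs, σ = 0.8 (assumed): P(T > 30) = 1 − Φ(ln(30/m)/0.8).

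| Assumed median (days) | Exponential | Of 36 | Lognormal | Of 36 |
|---|---|---|---|---|
| 5 | 0.016 | 0.6 | 0.013 | 0.5 |
| 7 | 0.051 | 1.8 | 0.034 | 1.2 |
| 10 | 0.125 | 4.5 | 0.085 | 3.1 |
| 14 | 0.226 | 8.2 | 0.170 | 6.1 |

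**4. Could the arms be observed for different times?** Observed time per patient is min(ICU stay, 30). For an exponential stay with mean m, its mean is m(1 − e^(−30/m)). The protocol gives no ICU stay by arm, so these means are also assumptions.
- m = 10: 10(1 − e^(−3)) = 9.50 days
- m = 12: 12(1 − e^(−2.5)) = 11.02 days
- m = 15: 15(1 − e^(−2)) = 12.97 days

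| Assumed mean stay, control / experimental | Mean observed days | Ratio, experimental to control (from unrounded values) |
|---|---|---|
| 10 / 10 | 9.50 / 9.50 | 1.00 |
| 10 / 12 | 9.50 / 11.02 | 1.16 |
| 10 / 15 | 9.50 / 12.97 | 1.36 |
| 15 / 12 | 12.97 / 11.02 | 0.85 |

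The difference may be nil or go either way.

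**The case against.** The strongest defence is that the window is a coherent choice. It extends 16 days beyond the last study-mandated ECMO procedure and matches the ICU/30-day frame used for daily data and concomitant medication. The two passages that state it agree, and it is the same in both arms. The endpoint is exploratory and descriptive, in a 72-patient feasibility pilot. Deaths are captured to hospital discharge and at 6 months, and SAEs that begin inside the window are followed afterwards. All of this stands and limits the weight of the point. It does not restore a non-fatal related event with late onset, or the attribution of a late death.

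Three stronger readings are tempting but not supported.
- *ECMO outlasts ICU discharge.* The weaning order in 8.1.2 speaks against this; only the day-30 limit is shown.
- *The arms are observed for unequal times.* The rule is identical and no ICU stay by arm is given, so this is a possibility of unknown direction. Nor would SAE counts simply follow observation time. Under 9.1 an event counts only if judged related to a study procedure, and the events of particular interest are mostly device or cannulation events, so the arms would differ whatever the window.
- *Transfer to an ECMO centre closes the window before cannulation.* Section 10.14 mentions "centres that do not perform ECMO but have access to an ECMO centre for backup", but it describes no transfer pathway and does not treat a move between ICUs as ICU discharge. Footnote 16 can be read as covering any ICU. A clarifying sentence is enough.

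A single extended window for patients on ECMO would also lengthen observation mainly in the experimental arm if those events were pooled with the rest. The fix has to keep them apart.

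**Conclusion.** The point holds in limited form. As written, the protocol does not require a related SAE to be reported if it first occurs on ECMO after day 30, or on the ward after ICU discharge but before day 30. This follows from the text and needs no assumption. Its size cannot be determined from the protocol. The range of about 1% to 23% of experimental patients (roughly 0.5 to 8 of 36) still on ECMO at day 30 rests on assumed median runs of 5 to 14 days, two assumed distributions and no deaths. It counts patients exposed beyond the window, not events missed.

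Unequal observation between arms is a risk, not a finding; ratios from 0.85 to 1.36 came out of the assumed stays. Neither issue undermines the feasibility objectives. The change is worth making because events that the protocol itself singles out can be lost, and no later analysis can recover them.

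**What to change.** Amend 9.4 and schema footnote 16 together:
1. In both arms, report related SAEs from randomization to day 30, or to death or hospital discharge if earlier, regardless of ICU discharge. Use this period for the between-arm description and give patient-days observed by arm.
2. For any patient in either arm still on ECMO at day 30, continue SAE reporting until decannulation or hospital discharge. List these events separately from the between-arm comparison.
3. State that transfer to another ICU does not end the window.

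This changes data collection only, not clinical management. The cost is a protocol amendment and a small amount of ward-stage chart review. Patients are already followed to hospital discharge, so no new visits are needed.
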